7.1.7. Additional Analysis of Adverse Events

The following categories of AEs of special interest will be summarized (number and percentage) by treatment group.

- Relapse of primary disease/chimerism
- CMV reactivation
- PJP (Pneumocystis Jiroveci Pneumonia)
- EBV reactivation
- Interstitial lung disease

7.2. Laboratory Evaluations

Laboratory data collected during the study will be analyzed and summarized using both quantitative and qualitative methods. Summaries of laboratory data will be provided for the Safety Analysis Set. The analysis will be based on values reported in conventional units. When values are below the LLOQ, they will be listed as such, and the closest imputed value will be used for the purpose of calculating summary statistics. Hemolyzed test results will not be included in the analysis, but will be listed.

A listing for laboratory test results will be provided by subject ID number and visit in chronological order for hematology and serum chemistry separately. Values falling outside of the relevant reference range will be flagged in the data listings, as appropriate. No inferential statistics will be generated.

7.2.1. Summaries of Numeric Laboratory Results

Descriptive statistics (n, mean, SD, median, Q1, Q3, minimum, and maximum) will be provided by treatment group for each laboratory test specified in the study protocol as follows:

- Baseline values
- Values at each post-baseline assessment
- Change from baseline at each post-baseline assessment

A baseline laboratory value will be defined as the last measurement obtained on or prior to the date/time of first dose of study drug. Change from baseline to a post baseline visit will be defined as the visit value minus the baseline value. Laboratory test results collected at unscheduled visits will be included for the baseline. The mean, median, Q1, Q3, minimum, and maximum will be displayed to the reported number of digits; SD to the reported number of digits plus 1.

In the case of multiple values in an analysis window, data will be selected for analysis as described in Section [3.8.3](#).

Tables of lab results will be based on double-blind data. OLE lab results will be included in the listings with a column indicating whether the lab result was reported during the OLE phase.

7.2.2. Graded Laboratory Values

The criteria specified in the study protocol will be used to grade laboratory results as Grade 0, mild (Grade 1), moderate (Grade 2), severe (Grade 3), or potentially life threatening (Grade 4). Grade 0 includes all values that do not meet criteria for an abnormality of at least Grade 1. Some laboratory tests have criteria for both increased and decreased levels; analyses for each direction (ie, increased, decreased) will be presented separately.

7.2.2.1. Treatment-Emergent Laboratory Abnormalities

Double blind phase treatment-emergent laboratory abnormalities are defined as values that increase at least 1 toxicity grade from baseline at any post-baseline time point, up to and including the earlier of the date of last dose of study drug plus 30 days, or the first dose of OLE study drug if any.

OLE phase treatment-emergent laboratory abnormalities are defined as values that increase at least 1 toxicity grade from OLE day 1 (first OLE dose date) at any post-OLE day 1 time point, up to and including the date of last dose of OLE study drug plus 30 days.

If the relevant baseline laboratory value is missing, any abnormality of at least Grade 1 observed within the time frame specified above will be considered treatment emergent.

7.2.2.2. Treatment-Emergent Marked Laboratory Abnormalities

Double blind phase treatment-emergent marked laboratory abnormalities are defined as values that increase from baseline by at least 3 toxicity grades at any post-baseline time point, up to and including the earlier of the date of the last dose of study drug plus 30 days, or the first dose of OLE study drug if any.

OLE phase treatment-emergent marked laboratory abnormalities are defined as values that increase from OLE day 1 (first OLE dose date) by at least 3 toxicity grades at any post-OLE day 1 time point, up to and including the date of the last dose of study drug plus 30 days.

If the relevant baseline laboratory value is missing, any Grade 3 or 4 values observed within the timeframe specified above will be considered treatment-emergent marked abnormalities.

7.2.2.3. Summaries of Laboratory Abnormalities

The following summaries (number and percentage of subjects) for treatment-emergent laboratory abnormalities will be provided by lab test and treatment group; subjects will be categorized according to the most severe post-baseline abnormality grade for a given lab test:

- Treatment-emergent laboratory abnormalities
- Treatment-emergent Grade 3 and 4 laboratory abnormalities
- Treatment-emergent marked laboratory abnormalities

For all summaries of laboratory abnormalities, the denominator is the number of subjects in the Safety Analysis Set with non-missing post-baseline values in the given study period.

A listing of all Grade 3 or 4 laboratory abnormalities will be provided by subject ID number and visit in chronological order. A column will indicate if the laboratory abnormality is treatment-emergent. This listing will include all test results that were collected throughout the study for the lab test of interest, with all applicable severity grades displayed.

7.3. Body Weight and Vital Signs

Body weight and vital signs (heart rate, systolic and diastolic blood pressure, body temperature, and respiratory rate) at baseline and each post-baseline assessment, and change from baseline in body weight and vital signs will be summarized for the Safety Analysis Set using descriptive statistics (n, mean, SD, median, Q1, Q3, minimum, and maximum) by treatment group. In the case of multiple values in an analysis window, data will be selected for analysis as described in Section 2. No formal statistical testing is planned. Only double-blind phase data will be summarized in tables. Both double-blind and OLE phase data will be included in listings.

7.4. Prior Medications and Concomitant Medications

Medications collected at screening and during the study will be coded using the current version of the World Health Organization (WHO) Drug dictionary. The medications will be categorized as prior or concomitant using the following definitions:

- Prior medications: any medications that were stopped before the study drug start date
- Concomitant medications: any medications initially taken on or after the study drug start date and up to 30 days after permanent discontinuation of study drug.

7.4.1. Prior Medications

Prior medications will be summarized by Anatomical Therapeutic Chemical (ATC) drug class and preferred name (using number and percent of subjects) by treatment group and overall. A subject reporting the same medication more than once will be counted only once when calculating the number and percentage of subjects who received that medication. The summary will be ordered by descending overall frequency of ATC drug classes and then by preferred names within an ATC drug class. For drugs with the same frequency, sorting will be done alphabetically.

Summaries will be based on the Safety Analysis Set. No inferential statistics will be generated.

For purposes of analysis, any medication with a stop date that is prior to or on the study drug start date will be included in the summary of prior medications. If a partial stop date is entered, then any medication with the month and year (if day is missing) or year (if day and month are missing) prior to the study drug start date will be included in the prior medications summary.

All prior medications (other than per-protocol study drugs) will be provided in a listing sorted by subject ID number and administration date in chronological order.

7.4.2. Concomitant Medications

Use of concomitant medications up to 30 days after permanent study drug discontinuation will be summarized by ATC drug class and preferred name (using number and percent of subjects) by treatment group. A subject reporting the same medication more than once will be counted only

once when calculating the number and percentage of subjects who received that medication. The summary will be ordered by descending active treatment group frequency of ATC medical classes and then by preferred names within an ATC drug class. For drugs with the same frequency, sorting will be done alphabetically.

Summaries will be based on the Safety Analysis Set. No inferential statistics will be generated.

For purposes of analysis, any medication with a stop date that is on or prior to the initial study drug dosing date or a start date that is after the last study drug dosing date plus 30 days will be excluded from a concomitant medication summary. If a partial stop date is entered, any medication with the month and year (if day is missing) or year (if day and month are missing) prior to the initial study drug dosing date will be excluded from the concomitant medication summary. If a partial start date is entered, then any medication with the month and year (if day is missing) or year (if day and month are missing) after the study drug stop date plus 30 days will be excluded from the concomitant medication summary. Medications with completely missing dates will be included in the concomitant medication summary.

All concomitant medications (other than per-protocol study drugs) will be provided in a listing sorted by subject ID number and administration date in chronological order.

7.5. Electrocardiogram Results

7.5.1. Investigator Electrocardiogram Assessment

Individual data for 12-lead ECG will be listed by subject and summarized by treatment group by incidence of events/abnormalities

7.6. Biomarker Analysis

No biomarker analyses are planned within the scope of this analysis plan. There will be a separate Biomarker Analysis Plan (BAP).

7.7. Changes From Protocol-Specified Safety Analyses

There are no deviations from the protocol-specified safety analyses.

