The primary analysis for BORR will be performed in the intent-to-treat (ITT) Analysis Set, which includes all subjects who were randomized. Response rate will be summarized by count and percent of subjects with each ordinal response (CR, PR, and CR + PR). A stratified Cochran-Mantel-Haenszel (CMH) Chi-square test will be performed to compare BORR between ENTO and PTM by 24 weeks. The difference in response rates between treatment groups and the corresponding 95% CIs will be presented.

Change from Baseline in the LSS scores will be analyzed using a mixed model repeated measures (MMRM) model. Duration of response (DOR) will be analyzed using the Kaplan-Meier method.

A sequential testing strategy will be implemented to preserve the overall type I error rate across the primary and key secondary endpoints of the study at a 2-sided significance level of 0.05. If the primary hypothesis is rejected, the key secondary endpoints will be sequentially tested at the 2-sided 0.05 significance level in the following order: (1) change from Baseline in the skin domain of the LSS, (2) change from Baseline in the mouth domain of the LSS, (3) change from Baseline in the eyes domain of the LSS, and (4) change from Baseline in the total score of the LSS. If a null hypothesis is not rejected, formal sequential testing will stop and only nominal significance will be cited for the remaining endpoints.

With 40 subjects per treatment group, there is 75% power to detect a 30% improvement in response rate at the 2-sided 0.05 significance level using a Fisher's exact test, assuming a placebo response rate of 50%. A total of 100 subjects (50 per treatment group) will be enrolled assuming a 20% dropout rate.

Safety data will be listed by subject and summarized by treatment and frequency of event/abnormality or descriptive statistical summaries, as appropriate. The endpoints to be evaluated will include AEs, physical examination, clinical laboratory test findings, ECG abnormalities and interval measurements, and vital signs measurements.

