1.2.1. Preclinical Pharmacology and Toxicology

Entospletinib (ENTO) was evaluated in a standard battery of safety pharmacology studies to assess potential effects on central nervous, cardiovascular, and respiratory systems. ENTO had no effect on central nervous and respiratory system parameters evaluated in rats. In a cardiovascular safety pharmacology study in dogs, small increases in heart rate (up to a 25% increase) were observed in male dogs given ENTO at 15, 50, or 150 mg/kg. While the higher heart rates were considered ENTO related, the relevance of these changes to humans is not known. Due to the observed increases in heart rate, a no observed effect level (NOEL) was not identified and the lowest observed effect level was 15-mg/kg. ENTO had no effect on ECGs or arterial blood pressure values at oral doses up to 150 mg/kg, the highest dose tested. Consistent with the lack of effect on ECG parameters, ENTO has no meaningful effect on the human-ether-a-go-go related gene (hERG), indicating that ENTO would not be expected to induce clinical QT prolongation.

The toxicity of ENTO has been characterized in animal genotoxicity, embryo-fetal reproductive toxicity, and phototoxicity studies. Recently published data demonstrated that species-specific GI toxicity and lymphoid changes, similar to that which was observed following ENTO administration to dogs, can occur in dogs but not rats, cynomolgus monkeys, or humans treated with p38 map kinase and mitogen-activated protein (MAP) kinase activated protein kinase-2 (MK2) small molecule kinase inhibitors that inhibit pathways that overlap with SYK signaling pathways {[Morris et al 2010](#)}. Oral administration of ENTO to rats for up to 26 weeks or cynomolgus monkeys for up to 39 weeks showed no evidence of GI toxicity or lymphoid changes at exposures which overlapped with or exceeded those that resulted in acute toxicity in dogs. Furthermore, ENTO (administered as Entospletinib methanesulfonate (ENTO MSA)) has been previously investigated in healthy human subjects at doses up to 1200 mg twice a day for 7 days and in subjects with rheumatoid arthritis (RA) at doses up to 900 mg twice a day for 26 days and no evidence of GI or lymphoid toxicity was observed in these clinical studies. Therefore, the relevance of these findings to humans is not known.

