8.6.4. Other Safety Evaluations

Individual data for 12-lead ECG, vital signs measurements will be listed by subject and summarized by treatment group by incidence of events/abnormalities or descriptive statistical summaries (n, mean, SD, median, Q1, Q3, minimum, and maximum), as appropriate. In comparison to pre-treatment (either Screening or pre-dose on Day 1) values, vital signs measurements and ECG findings will additionally be summarized using predetermined, clinically relevant thresholds.

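### SAP 7.7 says no protocol-specified safety analysis changed, but the threshold summaries of vital signs and ECG required by Protocol 8.6.4 are absent from the SAP

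*SAP*

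**What the plan says.** Protocol 8.6.4 sets two layers of analysis for ECG and vital signs. The first is a by-arm summary whose form is left open: "by incidence of events/abnormalities or descriptive statistical summaries (n, mean, SD, median, Q1, Q3, minimum, and maximum), as appropriate". The second is added to it, uses Screening or pre-dose Day 1 values as the reference, and has no such qualifier: "vital signs measurements and ECG findings will additionally be summarized using predetermined, clinically relevant thresholds". The safety paragraph of the Protocol Synopsis (Statistical Methods) also names the items to be evaluated: "physical examination, clinical laboratory test findings, ECG abnormalities and interval measurements, and vital signs measurements".

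For vital signs, SAP 7.3 says that "change from baseline in body weight and vital signs will be summarized for the Safety Analysis Set using descriptive statistics", and lists n, mean, SD, median, quartiles, minimum and maximum. Heart rate is included. For ECG, SAP 7.5.1 has one sentence: "Individual data for 12-lead ECG will be listed by subject and summarized by treatment group by incidence of events/abnormalities".

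SAP 7.7, the section meant to record departures from the protocol's safety analyses, reads in full: "There are no deviations from the protocol-specified safety analyses".

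**The concern.** The SAP omits an analysis that the protocol promises without condition, and then declares that nothing was omitted. A clinical study report that carries the 7.7 sentence forward would misinform its readers.

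A threshold table answers a question that by-visit descriptive statistics do not: how many subjects in each arm went past a stated limit at any time. For this drug the question has a specific basis. Protocol 1.2.1 reports that "small increases in heart rate (up to a 25% increase) were observed in male dogs", regards the higher rates as drug related, found no dose without the effect, and calls the relevance to humans unknown. Protocol 1.5 says that the placebo group helps the safety evaluation, and a by-arm count of outlying pulse values would use that comparison directly.

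**Working it through.** No arithmetic applies; the check sets the current protocol text against the current SAP text.

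| Item | Protocol | SAP | Result |
|---|---|---|---|
| Vital signs, descriptive statistics | 8.6.4 | 7.3, with SD, quartiles and extremes | Present |
| Vital signs against thresholds | 8.6.4, unconditional | None in 7.3 or elsewhere | Absent |
| ECG, incidence of abnormalities | 8.6.4, one of two permitted forms | 7.5.1 | Present |
| ECG against thresholds | 8.6.4, unconditional | None in 7.5.1 or elsewhere | Absent |
| ECG interval measurements | Synopsis only | No summary | Absent, but a weaker requirement |

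**Could the open wording in 8.6.4 excuse the threshold tables?** No. The latitude belongs to the sentence that offers incidence or descriptive statistics. The threshold sentence follows separately and adds to it.

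**Could the thresholds sit in another document?** Neither document says so. Where the SAP hands an analysis to another plan, as for biomarkers in 7.6, it states this.

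**Is the change disclosed elsewhere in the SAP?** In part. The revision log in SAP 11 (24 April 2018) records that the ECG analysis in 7.5.1 was reduced because the study was discontinued for lack of efficacy. The log entry covering 7.2.1 and 7.3 concerns only which study phase appears in tables and which in listings, and does not mention thresholds. The log records an update to 6.6, the efficacy counterpart of 7.7, but none to 7.7. An oversight is a plausible explanation. The contradiction does not depend on the log: it follows from 8.6.4 read against 7.3, 7.5.1 and 7.7 as they now stand.

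**Is 7.7 incomplete in any other respect?** Yes. Protocol 8.2.1.2 includes safety data up to 30 days after the last dose. SAP 3.1.2 stops at the earlier of that date and the first open-label dose. The change may be sensible, but it also belongs in 7.7.

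**What does the planned vital-sign table still show?** At each visit the maximum change shows that at least one subject reached a given value, and the SD and quartiles describe the spread. The table does not show how many subjects passed a limit, or how many did so at any visit during treatment.

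**The case against.** The strongest reply is that little is lost. Heart rate, the only nonclinical cardiovascular finding, keeps a full set of descriptive statistics by arm and visit, and vital signs are listed. A reader might infer that the SAP reports only means, so that outliers disappear. SAP 7.3 does not support that, since extremes and spread are shown. Only the count is missing.

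A reader might also infer that a required ECG interval analysis was dropped and that QT safety is in doubt. The documents do not support that strength of claim. Protocol 8.6.4 permits incidence alone, SAP 7.5.1 takes that option, and the interval requirement rests on the synopsis phrase "ECG abnormalities and interval measurements". Protocol 1.2.1 reports no ECG effect in dogs and no meaningful hERG effect. Nor was the ECG reduction concealed, because the revision log gives it with a reason.

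Abnormal vital signs or ECGs with signs or symptoms are recorded as adverse events if they meet the definition (Protocol 7.1.3). This cover is partial: a symptomless rise in pulse need not be captured that way.

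The study was stopped for lack of efficacy (SAP 2.3), and the protocol allows an abbreviated report (9.2.2). That can justify a smaller analysis, but it does not make the 7.7 statement true. Finally, the protocol never gives the thresholds, so cut-offs chosen now would be set after termination. This stands, and it should be stated openly with the table.

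**Conclusion.** The point holds in a limited form. Two summaries that Protocol 8.6.4 requires without condition, vital signs and ECG against thresholds, are not in the SAP, and 7.7 is wrong to say that nothing changed. The ECG reduction is disclosed only in the revision log, and the vital-sign omission is not disclosed at all.

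The practical loss is the by-arm count of subjects crossing a limit. It matters most for pulse, because of the dog finding, and less for ECG. The absent interval summary is secondary: it needs an entry in 7.7 if it is not produced, but 8.6.4 alone does not make it a deviation. No efficacy conclusion depends on any of this.

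The verdict assumes that no separate document, unmentioned in the protocol or SAP, defines the thresholds and commits to the tables. No numerical size can be given, because the documents contain neither cut-offs nor results.

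**What to change.** 1. In SAP 7.3, restore the by-arm threshold summary for vital signs, at least for pulse, relative to pre-treatment values. Fix the cut-offs before programming and state that they were set after termination.
2. In SAP 7.5.1, either restore the ECG threshold summary or list its omission in 7.7 with the reason.
3. Replace the 7.7 sentence with a list of every protocol-specified safety analysis that was changed or dropped, with reasons. Include the ECG simplification, the shortened safety window in 3.1.2 and, if they are not produced, the interval measurements named in the synopsis. Carry the list into the clinical study report.

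The cost is one or two standard tables and a few lines of text. No new data are needed for pulse, because Protocol Table 6-1 schedules vital signs at every visit. ECGs were scheduled at Screening, Week 24 and Week 48 or early discontinuation. If the tables are judged not worth producing after termination, item 3 is the minimum and costs wording only, provided that it also names the vital-sign threshold summary as dropped.

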8. PHARMACOKINETIC ANALYSES

The following tables will be provided:

- ENTO pharmacokinetic sampling details by subject including deviations in scheduled and actual draw times and procedures

10. SOFTWARE

SAS[®] Software Version 9.3. SAS Institute Inc., Cary, NC, USA.

11. SAP REVISION

Revision Date (DD MMM YYYY)	Section	Summary of Revision	Reason for Revision
24 APR 2018	2.3	Week 14 Analysis deleted	Study discontinuation due to lack of efficacy
24 APR 2018	2.4	Week 48 Analysis deleted	Study discontinuation due to lack of efficacy
24 APR 2018	2.5	Section number changed to 2.3. Added description of final analysis.	Study discontinuation due to lack of efficacy
24 APR 2018	3.1.2	Deleted the definition of Safety Analysis Set for OLE phase	Study discontinuation due to lack of efficacy and very few OLE AE occurrences
24 APR 2018	3.1.3	Deleted the immunosuppressant PK Analysis Set	Study discontinuation due to lack of efficacy
24 APR 2018	3.4	Deleted the specified subgroup analysis	Study discontinuation due to lack of efficacy
24 APR 2018	3.5	Deleted the multiple hypothesis testing	Study discontinuation due to lack of efficacy
24 APR 2018	3.6.1	Deleted the MMRM analysis for LSS. Moved the language of Lab value missing from section 3.7	Study discontinuation due to lack of efficacy
24 APR 2018	3.8.2	Added “for All Except ECG” at the end of title of Table 1	To clarify the windows apply to all endpoints but ECG
24 APR 2018	3.8.2	Deleted Table 3	Study discontinuation due to lack of efficacy and very few OLE AE occurrences
24 APR 2018	3.8.2	Added “FU-30 Day” nominal visit	To summarize the data more precisely
24 APR 2018	4.1	Deleted “Number and percentage of randomized subjects in the PP Analysis Set” and “The reasons for exclusion from the PP Analysis Set will be summarized separately”	Study discontinuation due to lack of efficacy
24 APR 2018	4.2.2	Changed the formula of calculating adherence	The PPI usage is not recorded in the eCRF thus day based formula is used to calculate adherence
24 APR 2018	6.3	Added the missing imputation when the entire NIH questionnaire is missing	To clarify the missing imputation
24 APR 2018	6.4.2	Deleted the MMRM analysis	Study discontinuation due to lack of efficacy
24 APR 2018	6.5.1	Deleted two exploratory endpoints related to flares	Study discontinuation due to lack of efficacy and very few flares

24 APR 2018	6.5.2	Deleted the time to first flare analysis and methods handling multiple occurrences	Study discontinuation due to lack of efficacy and very few flares
24 APR 2018	6.6	Added all new changes to the section	Study discontinuation due to lack of efficacy
24 APR 2018	7.1.5.1	Clarify the definition of treatment emergent	To clarify the definition of treatment emergent
24 APR 2018	7.1.6	Updated the list of summaries of AEs	To provide TFLs for CSR
24 APR 2018	7.1.7	Deleted the language of using SMQ method	Some AEs of interest are not defined based on SMQ
24 APR 2018	7.2.1 7.3	Clarify only double blinded phase data will be present in table. Listing will include both double blinded phase and OLE data	To clarify the inclusion of data and there are very few data in OLE
24 APR 2018	7.5.1	Simplified the analysis for ECG	Study discontinuation due to lack of efficacy
24 APR 2018	7.6	Deleted the biomarker analysis	There will be separate analysis regarding biomarker
24 APR 2018	8	Deleted the table for PK analysis	Study discontinuation due to lack of efficacy
24 APR 2018	Appendix 2	Deleted the sub study schedule of assessment	Study discontinuation due to lack of efficacy
24 APR 2018	Appendix 6 Appendix 7	Deleted MMRM and negative binomial model	Study discontinuation due to lack of efficacy

